### 6.1.2 Health coaching

Participants will receive two health coaching sessions, lasting up to 60 minutes, delivered by telephone or videoconference as preferred by the participant. The health coach will be a tertiary-qualified physiotherapist or other health professional trained and experienced in delivering empowerment-focused coaching to facilitate physical activity behaviour change. The first coaching session will take place within 2 weeks of randomisation, and the second session four weeks after the first. This person-

centred health coaching approach will provide information and education. The sessions will also draw on evidence-based behaviour change techniques, practice and theories to help participants set goals, action plan, and provide accountability through prompting, monitoring and reinforcement. The coach's role is to work with participants to make achievable choices, reinforce and evaluate progress, and facilitate accountability.

### **6.1.3 Email or SMS Behaviour Change Messages**

Participants will choose the type of message platform and the frequency at which they would like to receive motivational messages over the 6-month period. Participants will choose between receiving unidirectional email messages that are delivered either weekly (24 emails), fortnightly (12 emails) or monthly (6 emails) frequencies over the 6-month period; or receiving SMS messages that are delivered once per week (24 SMS messages), twice per week (48 SMS messages), or three times per week (72 SMS messages) over the 6-month period. The emails and SMS messages will include several behaviour change techniques (BCTs). Both the email and SMS messages will deliver similar content informed by behaviour change theories. Secure marketing websites will be used to send the email messages and SMS messages.

### **6.1.4 Active Women over 50 Website**

The website will emphasise the importance of becoming active from middle age for maintenance of health and physical function and prevention of falls in older age. Content will include three main pages (see Figure 2 below): "Why be active?", "How to be active", and "Be inspired". The "Why be active?" page includes evidence-based information about the effect of physical activity in middle-age to maintain health, longevity, and prevent disability in older age. The "How to be active" page includes practical suggestions for becoming more active using behaviour change techniques such as SMART goal setting, self-assessment of barriers to physical activity and solution-generation and included links to resources supporting habit formation and behaviour change, and information for different health conditions and services. The "Be inspired" page includes role modelling content to inspire participant's motivation to be physically active through video case studies and photo stories of "real life" women over 50, external podcasts, and blog posts. Participants will have the ability to access the website at their own discretion. Examples will reflect diversity of participant characteristics and place of residence (i.e., urban, regional, rural, remote).

[figure not shown]

Figure 2. Screenshots of the Active Women over 50 website

### 6.1.5 Active Women over 50 private Facebook group

Participants will have access to a private Facebook group to support networking and social support (see Figure 3 below). Participants will be able to post comments to a common page (i.e., the group wall); view and respond to others' posts; create and post to discussion boards; and post web links, photographs, and videos. The private Facebook group will be moderated daily (Monday to Friday) by a member of the research team to ensure interactions are appropriate and relevant. Participants will be informed of the group rules, which will be both posted in the group, and pinned to the top of the group webpage. Only participants receiving the intervention will be granted access to the private Facebook group.

Figure 3. Screenshot of the Active Women over 50 private Facebook group page

## 6.2 Primary and Secondary Outcome Measures

**Primary outcome:** The average number of daily steps at 6 months after randomisation, measured objectively with an ActiGraph accelerometer.

**Secondary outcomes:** The secondary outcomes will be: Self-reported and device-measured physical activity, self-reported falls, mental wellbeing, physical function, quality of life, bodily pain, menopause symptoms, sleep, balance, fear of falling, action planning and coping planning at baseline, proportion achieving device-measured light physical activity and lower limit MVPA/week, and proportion who increased their daily steps by 2000+, measured with an ActiGraph activity monitor at 6 months after randomisation, and individualised goal attainment at 6 months after randomisation.

Additional secondary outcomes for the intervention group participants at 12 months after randomisation will be: self-reported falls, mental wellbeing, physical function, quality of life, bodily pain, menopause symptoms, sleep, balance, fear of falling, action planning and coping planning, proportion achieving device-measured light physical activity and lower limit MVPA/week, and proportion who increased their daily steps by 2000+, measured with an ActiGraph activity monitor at 12 months after randomisation, the average number of daily steps at 12 months after randomisation, measured with an ActiGraph activity monitor.

### 6.2.1 Assessment of primary outcomes

Physical activity will be assessed at baseline, and 6 months after randomisation over a seven-day period using a matchbox-sized accelerometer (ActiGraph GT3X+) worn on a belt at the hip or wrist. The device accurately estimates how physically active a person has been throughout the day by measuring 3D body accelerations. The data will be collected over a 7 day period to account for day-to-day variation in physical activity levels as per protocol from a previous trial. The accelerometers will be posted to participants with clear instructions for use and telephone support will be available. Participants will be provided with pre-paid envelope to return the device to the research centre.

### 6.2.2 Assessment of secondary outcomes

The secondary outcomes will be assessed at baseline, and six months post-randomisation using self-report surveys and an accelerometer (ActiGraph GT3X+) (See Table 2) and will take approximately 20 minutes to complete. Additional secondary outcomes for the intervention group participants will be assessed twelve months post-randomisation in a similar manner with survey and accelerometer as described for the six-month follow-up. The Table 3 presents the schedule of assessments.

**Table 2: Study secondary outcomes and measures**

Secondary effectiveness outcomes	Measure
Self-reported physical activity	Single-item physical activity question (In the past week, on how many days have you done a total of 30 minutes or more of physical activity, which was enough to raise your

	
breathing rate. This may include sport, exercise, and brisk walking or cycling for recreation or to get to and from places, but should not include housework or physical activity that may be part of your job”)
 
Frequency of participation in strength training and balance training

Falls rate	Monthly falls calendar
Mental wellbeing	Warwick-Edinburgh Mental Well-being Scale 
Physical function	PROMIS SF v2.0 – Physical Function 4a
Quality of life	EuroQol EQ-5D-5L 
Bodily pain	PROMIS SF v2.0 – Pain interference and Pain intensity 4a
Sleep	Pittsburgh Sleep Quality Index (PSQI) 
Balance	Perception of balance: (“Do you feel your balance is excellent, very good, good, fair, poor”)
Menopause symptoms	The Menopause-Specific Quality of Life Questionnaire
Fear of falling	(“Are you afraid of falling? (1 = not at all, 2 = little bit, 3 = moderately, 4 = quite a lot, 5 = extremely”)
Proportion achieving light physical activity and lower limit MVPA/week	Actigraph accelerometer
Proportion of people who increase their daily steps by 2000+ from baseline to 6 and baseline to 12 months after randomisation	Actigraph accelerometer
The average number of daily steps at 12 months after randomisation	ActiGraph accelerometer
Action Planning and Coping Planning	Action Planning and Coping Planning questionnaire 
Individualised goal attainment	Goal Attainment Scale at 6 months after randomisation

**Table 3 Schedule of assessments**

--	--

TIME POINT	-t 1	0	t 1	t 2	t 3	Monthly
ENROLMENT:						
Eligibility screen	✓					
Informed consent	✓					
Baseline surveys, Device measured activity Actigraph	✓					
Randomisation / Allocation		✓				
INTERVENTIONS:						
Active Women over 50 program		✓				
Waiting list control				✓		
OUTCOMES						
Number of falls measured with monthly calendars for 6 months						✓
Device-measured outcomes using Actigraph	✓		✓		✓	
Individualised goal attainment	✓		✓			
Self-reported secondary outcome measures	✓		✓		✓	

-t1: baseline, prior randomisation; 0: after randomisation, t1: 6-month follow-up; t2: after 6-month follow-up completed; t3: 12-month follow-up for intervention group participants

### 6.3 Cost-effectiveness outcomes

The cost of delivering the intervention and total costs of health and community service utilisation will be calculated for the cost-effectiveness analysis. Intervention costs will be estimated based on trial records where the resources required to implement the intervention will be recorded (e.g. staff time, any additional non-staff resources) and costed using appropriate wage rates and other relevant cost data. Healthcare and community-service utilisation will be collected over the trial period (6 months) on a monthly basis and costed using standard cost data such as IHPA, NHDC and Medicare unit costs.

The main effectiveness outcomes of the economic evaluation will be physical activity (average steps per day measured with an ActiGraph), falls, physical function, and utility-based quality of life six months after baseline.

Utility-based quality of life will be measured using the EQ5D-5L and the health utility score, which is expressed as an index value for health, will be calculated from the 5 questions using published Australian scoring algorithms. The scores fall on the 0.0 (dead) to 1.0 (perfect health) value scale.

Quality-adjusted life years (QALYs) will be calculated using the health utility score at baseline and 6-month follow-up. The number of QALYs gained or lost over the 6 months of follow-up will be calculated by multiplying the time spent in the health state by the relevant health utility score.

#### **6.4 Process evaluation and implementation**

The process evaluation is embedded in this study. Quantitative and qualitative methods will be used to assess the degree of successful program implementation (including reach the resources and intervention components used, type of message platform used/accessed), and the potential areas for improvement in relation to the intervention and its implementation. Implementation and scale-up considerations are described in Table 4.

In terms of acceptability, barriers and facilitators, participants' experiences of the intervention will be explored via post-intervention 'Impressions' surveys (sent to all intervention group participants once they complete the program) and semi-structured interviews with up to 30 purposively sampled participants, selected for maximum variation in age, geographical location, socio-economic status, carer responsibilities and engagement with the intervention (as reported in their Impressions survey). Questions in the survey and interviews cover attractions and expectations of the intervention, views of the intervention and its four components, any impacts, accounts of continuing/discontinuing participation, and questions related to the underlying program theory phrased in lay language. Survey and interview questions will be tested with consumer representatives and amended as required in line with their feedback prior to use in the trial. Qualitative data from free text comments in the surveys, and from transcriptions of the semi-structured interviews, will be analysed thematically. A workshop will be held with those involved in implementing the intervention to collate experiential views about what worked well and areas for improvement. The relationship between insights gained from qualitative analysis and trial outcomes will be explored.

If the intervention is effective, this process evaluation information will be used to guide future intervention design, for implementation at scale, including approaches for different participant profiles and contexts.

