### **3.2 Secondary Objectives**

Secondary aims are (1) to evaluate the effectiveness of the Active Women over 50 program on physical activity, falls, mental wellbeing, physical function, quality of life, sleep, bodily pain, menopause symptoms, balance, fear of falling, action planning, and coping planning at 6 months after randomisation; (2) to evaluate the effectiveness of the Active Women over 50 program on goal attainment at 6 months after randomisation; (3) to evaluate the proportion of participants who i) achieve light physical activity and lower limit MVPA/week, ii) increase their daily steps by 2000+ from baseline to 6 months after randomisation; (4) to explore the experiences of participants of the Active Women over 50 program and to investigate contextual factors that affect the program uptake and maintenance; (5) to assess the cost-effectiveness, implementation potential and determinants to guide scale-up from the perspective of the healthcare and community funder; (6) to test secondary implementation outcomes (reach, fidelity and adoption, dose, sustainability); (7) To evaluate the number of daily steps for intervention participants 6 months after the program has ended, at 12 months after randomisation; (8) to evaluate the effect of the Active Women over 50 program on physical activity, falls, mental wellbeing, physical function, quality of life, sleep, bodily pain, menopause symptoms, balance, fear of falling, action planning, and coping planning for intervention participants 6 months after the program has ended, at 12 months after randomisation; (9) to evaluate the proportion of intervention participants who i) achieve light physical activity and lower limit MVPA/week, ii) increase their daily steps by 2000+ from 6 to 12 months after randomisation.

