## **4 STUDY DESIGN**

### **4.1 Type of Study and Participants**

This study will use a two-arm parallel pragmatic hybrid type I effectiveness-implementation randomised controlled trial (n=1000) to test the effectiveness of the Active Women over 50 program on daily steps at 6 months compared with wait-list control among women aged 50+. In addition, a process evaluation will be undertaken to explore the experiences of participants in the intervention group after completing the program through interviews of approximately 30 participants and the impressions survey completed by all intervention group participants at 6-month follow-up. An economic analysis will also be carried out to evaluate cost-effectiveness, considering the perspective of both healthcare providers and community funders. The impact of the Active Women over 50 program on physical activity and secondary outcomes, 6 months after the program has ended, will be evaluated for intervention group participants 12 months after randomisation.

Participants will be randomly allocated in equal numbers to:

- a) Immediate participation in the 6-month Active Women over 50 program (intervention group), n=500 or
- b) Delayed participation in the Active Women over 50 program, waitlist control (control group, n=500)

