**Table 4: Implementation outcomes**

Outcomes	Definition as per McKay et al 2019 	Measurement tool
Reach	Proportion of the intended priority audience (i.e., participants) who participate in the intervention	Screening survey from recruitment website; baseline data form.
Adoption	Proportion and representativeness of providers or the delivery team that deliver an intervention	Study specific document maintained by trial manager; screening survey from recruitment website.
Fidelity	The extent to which an intervention is implemented as it was prescribed in the intervention protocol - by the delivery team	Study specific records
Dose (delivered)	Intended units of each intervention component delivered to participants by the delivery team	Study specific records
Determinants		
Acceptability (delivery team)	Perceptions among the delivery team that a given intervention is agreeable, palatable, or satisfactory	Qualitative interviews/ focus groups with delivery team
Acceptability (participants)	Perceptions among the participants that a given intervention is agreeable, palatable, or satisfactory	Includes 1. Study-specific documents on intervention components (e.g., agreement and participation in health coaching sessions); 2. data from message services on number who unsubscribe from messages, number messages opened; 3. Google analytics on website usage; 4. Engagement on Facebook; 5. Quantitative survey rating different elements of intervention; 6.

		Qualitative interviews with sub-group participants.
Cost	Money spent on design, adaptation, and implementation of an intervention	Study-specific log recording costs
Feasibility	Perceptions among the delivery team that an intervention can be successfully used or carried out within a given organisation or setting	Qualitative interviews/ focus groups with delivery team
Context	Aspects of the larger social, political, and economic environment that may influence intervention implementation	Field notes kept by Research Manager based on Consolidated Framework for Implementation Research (CFIR)
Adaptability	Extent to which an intervention can be adapted, tailored, refined, or reinvented to meet local needs	Study-specific document guided by expanded Framework for Reporting Adaptations and Modifications to Evidence-based interventions (FRAME) framework (Wiltsey Stirman et al Imp Sci 2019)

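### Interviewees are selected on engagement self-reported in a post-program survey, so accounts of uptake and stopping will lean towards completers and survey responders

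*Protocol*

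**What the plan says.** Secondary objective 4 (Protocol section 3.2) is to explore participants' experiences and "to investigate contextual factors that affect the program uptake and maintenance". Section 6.4 serves it with an Impressions survey and with "semi-structured interviews with up to 30 purposively sampled participants, selected for maximum variation in age" and other characteristics. The last of these are "socio-economic status, carer responsibilities and engagement with the intervention (as reported in their Impressions survey"). The survey and interviews are to cover, among other topics, why women carried on or stopped.

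The protocol describes the distribution of the survey in two ways. Section 6.4 says it is "sent to all intervention group participants once they complete the program". Section 4.1 refers to "the impressions survey completed by all intervention group participants at 6-month follow-up", although it also states the aim of the process evaluation as "to explore the experiences of participants in the intervention group after completing the program".

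Table 4 lists sources on participant acceptability that do not depend on the survey. The first is "Study-specific documents on intervention components (e.g., agreement and participation in health coaching sessions"). It also lists message opening and unsubscribing, website analytics and Facebook activity. Section 6.4 does not use any of these to select interviewees.

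**The concern.** Engagement is the one selection criterion meant to bring in women who used the program little or gave it up. Its value is taken from a questionnaire issued at the end of the program, so it exists only for women who answer. Failure to answer is likely to go with low engagement, so the criterion is probably missing most often where it is needed most.

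Section 6.4 intends to use this evidence, if the program is effective, to shape delivery at scale and to adapt it to different kinds of participant. If interviewees are mostly women who finished and responded, acceptability may look better than it is, and reasons for non-use may be under-represented. The primary outcome and the other quantitative comparisons are not affected.

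**Working it through.** The protocol states no figure for this point, so there is nothing to reproduce. The check sets the relevant sections side by side and asks which intervention women could be selected on engagement.

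**Step 1: who receives the survey.** Section 6.4 ties dispatch to completing the program, and section 4.1 ties completion of the survey to the 6-month visit and to all intervention women. The two agree only if completing the program means reaching 6 months. The protocol does not say so and gives no criterion for completion.

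**Step 2: who remains contactable.** Section 6.5.2 continues follow-up of women who depart from the intervention protocol, and rules out further data collection from women who withdraw from the study. It also allows the primary outcome alone to be sought as a last resort. A low engager may therefore supply accelerometer data and no Impressions survey.

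**Step 3: four groups of intervention women.**

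- *Finished the program and returned the survey.* Selectable on engagement under either section.
- *Low use or stopped early, still in follow-up, returned the survey.* Selectable if the survey goes to everyone at 6 months (section 4.1). On a literal reading of section 6.4 she might not be sent it.
- *Not withdrawn, survey not returned.* No engagement value under either section. She could still be invited for her age or location, but not because she engaged little. Table 4 nevertheless provides for a record of her coaching participation.
- *Withdrawn from the study.* Outside any interview frame under section 6.5.2, whatever the selection rule.

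The third group is lost to engagement-based selection on every reading and could be recovered by using records. The second depends on reconciling sections 4.1 and 6.4. The fourth cannot be recovered.

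**Step 4: size.** Sizing the second and third groups would need the return rate of the Impressions survey and the share of non-withdrawn women who use the program little or stop. The protocol gives neither.

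**The case against.** The strongest reply is that the protocol plainly means to include low engagers. Section 4.1 has all intervention women completing the survey at 6 months. The program is a fixed 6-month offer with message frequency chosen by the participant (section 6.1.3) and website use left to her (section 6.1.4), so completing it most naturally means that the 6 months have elapsed. Section 6.5.2 keeps following women who depart from it. Engagement is named as a dimension of variation, and stopping is a topic of the interviews. A woman who skipped coaching but answers the survey can report low engagement and be chosen for it. All of this stands.

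Three stronger readings are tempting, and the documents do not support them.

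- A reader might infer that women who never took up the program or stopped are left out altogether. That is certain only for those who withdraw. Non-responders are lost only to selection on engagement.
- A reader might infer that objective 4 cannot be answered. It also draws on usage records, free text in the survey, an implementers' workshop and field notes on context. These show who stopped and in what setting, though the usage records and field notes do not give a woman's own reasons.
- A reader might apply the 25% dropout in section 7.1 to the arm of 500 and count the resulting women as missing from the interviews. That percentage is a sample-size allowance, not survey non-response. Section 6.5.3 gives 20% and calls it higher than expected. Either figure would include withdrawn women, who cannot be interviewed in any case. Nor does a purposive sample allocate places in proportion.

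Maintenance might also be read as activity after support ends, which would call for interviews at 12 months. Objective 4 speaks of the program's uptake and maintenance, and objectives 7 to 9 address the 12-month period quantitatively. The absence of 12-month interviews is therefore not a fault.

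What the reply does not meet is the non-withdrawn woman who does not return the survey. The protocol itself names both the selection variable and its source, so this is not a detail left to a later document.

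**Conclusion.** The point holds as a risk of selection bias in the qualitative sub-study. Interviewees are chosen on self-reported engagement from an end-of-program survey, so non-withdrawn women who do not return it cannot be chosen on engagement, and accounts of barriers and of stopping will lean towards completers and responders. Objective 4 is answered with that tilt; it is not left unanswerable. The wording of sections 6.4 and 4.1 on who is sent the survey, and when, also needs reconciling.

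The number of women concerned cannot be derived from the protocol. The direction of the bias rests on one assumption, that women who do not return the survey tend to be less engaged than those who do. This is plausible, but the protocol does not show it. The change is worth making because it is cheap and because accounts of stopping become harder to collect once the 6-month contact has passed.

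**What to change.** 1. Reconcile sections 6.4 and 4.1 so that the Impressions survey goes to every intervention participant who has not withdrawn, at 6 months, whatever her participation.
2. In section 6.4, select interviewees on recorded engagement, in place of self-report or in addition to it. Coaching attendance is the obvious measure. Message records can be added if they are held per person; Table 4 describes them as counts, so this needs checking.
3. Within the same total of about 30, state a minimum number of low or non-engagers and survey non-responders who have not withdrawn.

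The cost is a protocol amendment, which section 10.2 sends to the ethics committee before it takes effect, and some adjustment to the invitation process. The number of interviews does not change, and coaching participation is already to be recorded. Less engaged women will probably accept less often, so more invitations will be needed per completed interview, and slightly fewer places will remain for variation in age, location, socio-economic status and caring role.
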